2 INTRODUCTION

Note: in this document any text taken directly from the non-interventional (NI) study protocol is *italicised*.

The treatment of metastasized renal cell carcinomas (mRCC) has radically changed within short time. During the last years several new substances for the treatment of mRCC have been launched and have raised new scientific questions. Temsirolimus and Sunitinib are the current standard therapy options in the first-line treatment of mRCC. Inlyta®represents a new therapy option in mRCC patients after failure of Sunitinib or cytokines.

Since August 2009 Torisel[®] is available as another therapy option for patients with MCL. Sunitinib[®] is also suitable for the second-line therapy of patients with gastrointestinal stromal tumors (GIST).

In April 2016, the first immunoocologial therapy (Nivolumab) received approval for treatment of mRCC in adults. Furthermore, in August 2016, the combination Lenvatinib / Everolimus was approved as therapy for mRCC patients after a therapy targeted against-VEGF and in September 2016 Cabozantinib gained approval for patients with mRCC after a previous therapy targeted against VEGF.

As the treatment options have significantly changed for mRCC – as reflected in the current S3-guideline – data on the use of sunitinib followed by the new therapy options followed by axitinib in daily routine is missing. This holds regarding information on efficacy and tolerability of axitinib as third or higher line therapy.

In amendment VII it is stated to reduce the recruitment period by 12 months, as the primary application of Sunitinib[®] in the therapy sequence moves towards later lines of therapy due to new approvals of ICI in combination with other ICI or TKI. This also

results in later lines for the interim therapies and $Axitinib^{@}$. Analyses of patient recruitment and number of subjects included into each documentation cycle showed, that the additional study objective defined in amendment VI will not be reachable within the planned study period.

2.1 STUDY DESIGN

The registry STAR-TOR is a prospective, multicenter, open-label, non-interventional observational study (registry).

At a baseline visit eligibility of patients will be checked and baseline information will be documented. Patients treated will be followed up at visits every 8 to 12 weeks until treatment with temsirolimus, sunitinib or axitinib. was discontinued or documentation was stopped for any reason. For subjects with ongoing documentation survival information on the patients should thereafter be documented 12 months after baseline and then every six months until the patient dies or cannot be reached for other reasons. After the first documented sequence with any of the three Pfizer therapies, for patients suffering from mRCC the documentation of non Pfizer-products may follow. This documentation is much smaller with regard to content and should be filled out every 8 to 12 weeks. If another Pfizer treatment is given thereafter (in 3rd line or higher) sequences of the three therapies sunitinib, temsirolimus and axitinib can be documented. In this case the documentation will be continued with further follow-up documentations after documentation of a discontinuation form. Survival information will then be documented after the second therapy.

Detailed information on assessments for patients suffering from mRCC are presented in the following flow chart. For patients suffering from GIST or MCL documentation ends after end of first sequence.

Statistical Analysis Plan

Flow chart on documentation sequences for patients suffering from mRCC

	1 st Pfizer therapy sequence		Documentation of treatment with non-Pfizer therapies 2 nd Pfizer therapy sequence			Survival information		
	Baseline visit	Follow- up visit every 8 – 12 weeks	Final / discontinuation of treatment	every 8 – 12 month	Baseline at time of start of 2 nd Pfizer therapy	Follow- up visit every 8 – 12 weeks	Final / discontinuation of treatment	12 month after discontinuation and then every 6 months
Demography	X	X	X		X	X	X	X
In- and exclusion criteria	X							
Patient consent	X			(x)				
Tumor anamnesis	X				X			
Karnofsky Performance status / height / weight	х	X			х	X		

Therapy / Medication								
Prior medication	X							
Concomitant medication	X				X			
Tumor treatment	X	X		X	X	X		X
Safety								
Concomitant diseases / physical examination	X				x			
Laboratory values	X	Х			Х	Х		
Blood pressure	X	X			X	X		
ECG	X	X			X	X		
Echocardiogram	X	X			X	X		
Assessment of pain	X	х			Х	Х		
Adverse events	X	X	X	X	X	X	X	

Efficacy								
Risk prognosis	X				X			
CT / MRT	X	X				X		
Ultrasound	X	X				X		
Chest X-ray	X	X				X		
Tumor assessment		X		X		X		
Physician's assessment of efficacy and tolerability		x				X		
Physician's overall assessment of treatment response			X	Х			X	
PRO: quality of life	X	Х			X	X		

Study population

It is planned to recruit 100 patients per year and treatment over a total recruitment period of 156 months, resulting in approximately 1.600 patients in summary. Patients should only be included after physician's decision to treat the patients with either Torisel®, Sutent® or Inlyta®.

2.2 STUDY OBJECTIVES

The objective of this registry study is to obtain a general impression regarding questions on efficacy, tolerability and safety of a temsirolimus, sunitinib or axitinib therapy in patient with advanced renal cell carcinoma, recurrent/refractory mantle cell lymphoma (rMCL) and GIST under routine treatment conditions in usual care. The therapeutic armamentarium for the management of advanced RCC is significantly changing and thus, for example, there is a lack of real-world data concerning the routine use of sunitinib followed by new therapeutic options followed by axitinib in order to assess the efficacy and safety of axitinib in third or later lines appropriately.

The following information is of particular interest in the course of the therapy:

- Safety profile (overall incidence of adverse events and side effects) of patients with mRCC, rMCL and GIST treated receiving temsirolimus, sunitinib or axitinib.
- *Tolerability of the therapy (assessment performed by treating physician)*
- Effectiveness (maximum response, survival time, progression-free survival)
- Profile, comorbidities and characteristics of patients treated with temsiolimus, sunitib or axitinib.
- Sequences used for systemic therapies of patients with RCC, MCL and GIST.
- Patient questionnaires regarding quality of life of patients suffering from mRCC.

3 INTERIM ANALYSES

Two interim analyses are planned per year. A final analysis after end of study is planned with identical content. The analyses to be performed and the tables to be presented are defined in this statistical analysis plan (SAP).

Interim analyses are performed in order to get and to present early information on safety and effectiveness of a treatment with temsirolimus, sunitinib or axitinib in the usual health care setting. Interim analyses are also performed in order to get answers on new scientific questions.

4 HYPOTHESES AND DECISION RULES

4.1 STATISTICAL HYPOTHESES

Not applicable.

4.2 STATISTICAL DECISION RULES

Not applicable.

5 ANALYSIS SETS/POPULATIONS

Analyses will be performed within each indication and treatment, e.g. one for mRCC and temsirolimus, sunitinib and axitinib, one for the non-Pfizer interim therapies and one for MCL and one for GIST.

For data from mRCC patients included prior to amendment VI of the protocol baseline data from sequence 1 will be forwarded as baseline data for sequence 2, if the respective data is not asked for in follow-up 1 of sequence 2 (tumor anamnesis at time of primary diagnosis, prior local and systemic therapies, prior and concomitant diseases, concomitant medication (other than systemic therapy)). Ongoing adverse events from sequence 1 have to be added to the list of concomitant diseases in sequence 2. Additional cancer therapy from baseline and follow-up visits of sequence 1 will be forwarded as baseline data for sequence 2 unless the therapy has been discontinued.

For patients included under amendment VI, baseline data for the second Pfizer treatment will be asked for in the CRF as changes in this data are not completely asked for in the non-Pfizer treatment periods.

For data from mRCC patients the following tables (see chapter 9): demographic information (1.2-1; 1.2-2), study periods (1.1-5.2), previous local and systemic therapy (1.5-1; 1.5-2), duration of therapy (1.6-1), overall survival (2.2-1), progression free survival (2.3-1), course of Karnofsky performance scale (2.5) and course of FKSI-15 (2.6), EQ-5D (2.7) will be repeated for the following groups of patients:

- Treatment sequence 1^{st} sunitinib $\rightarrow 2^{nd}$ axitinib \rightarrow any further therapy
- Treatment sequence 1^{st} temsirolimus $\rightarrow 2^{nd}$ sunitinib \rightarrow any further therapy
- Treatment sequence 1^{st} sunitinib \rightarrow any further therapy (no axitinib in 2^{nd} line)
- Treatment sequence 1^{st} temsirolimus \rightarrow any further therapy
- Treatment sequence 1^{st} sunitinib \rightarrow no further therapy
- Treatment sequence 1^{st} temsirolimus \rightarrow no further therapy
- Any therapy $\rightarrow 2^{\text{nd}}$ axitinib \rightarrow any further therapy.

The following treatment sequences were included on the basis of amendment VI. Following the rationale in amendment VII, it was not possible to include a sufficient number of subjects for meaningful statistical conclusions. Thus no analyses will be performed for this treatment sequences, but data on demographic information, previous local and systemic therapy, duration of therapy (by Pfizer therapy, by non-Pfizer

treatment), overall survival, progression free survival, course of Karnofsky performance scale, course of FKSI-15 and EQ-5D will be listed.

- Treatment sequence 1st Pfizer treatment \rightarrow non-Pfizer treatment \rightarrow 3rd line axitinib
- Treatment sequence 1st fizer treatment \rightarrow non-Pfizer treatment 1 \rightarrow non-Pfizer treatment 2 \rightarrow (possibly more non-Pfizer treatments) \rightarrow 4th line or later axitinib

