7.2. Study Setting

Inclusion and exclusion criteria:

- a) Patients with a histologically confirmed diagnosis of advanced renal cell carcinoma without prior therapy and at least 3 of 6 prognostic risk factors or relapsed/refractory mantle cell lymphoma for whom a decision was already made to treat with temsirolimus.
- b) Patients with histologically confirmed diagnosis of advanced/metastatic renal cell carcinoma or unresectable and/or metastatic GIST, after imatinib failure, for whom a decision was already made to treat with sunitinib.
- c) Patients with histologically confirmed diagnosis of advanced renal cell carcinoma after failure of prior therapy with sunitinib or a cytokine for whom a decision was already made to treat with axitinib.
- d) Written informed consent form from the patient is obtained prior to enrollment into the registry.

Due to the non-interventional nature of the registry, no specific requirements apply regarding the management of treatment. Dosing and duration of treatment will be decided by the physician according to individual treatment requirements of the patient.

Extract from the Summary of Product Characteristics

During the treatment of patients with temsirolimus, sunitinib, and axitinib, among other things, the section "Contraindications" of the respective Summary of Product Characteristics must be taken into account. In case of hypersensitivity reactions, the advice in the relevant Summary of Product Characteristics must be observed.

[figure not shown]
- a) In particular, the following excerpts are included under Section 4 "Clinical particulars" of the Summary of Product Characteristics of temsirolimus:
 - Hypersensitivity to the active substance or to any of the excipients of temsirolimus
 - It is recommended that patients be given an H1 antihistamine before an infusion of temsirolimus. In case of known hypersensitivity to antihistamines or in patients who cannot receive an antihistamine for another medical reason, temsirolimus should be used with caution.
 - Concomitant use of substances that affect CYP3A metabolism: CYP3A4 inducers: e.g. dexamethasone, carbamazepine, phenytoin, phenobarbital, rifabutin, rifampicin, St John's wort
 - CYP3A4 inhibitory agents: e.g. atazanavir, clarithromycin, indinavir, itraconazole, ketoconazole, nefazodone, nelfinavir, ritonavir, saquinavir, telithromyzine.
 - Concomitant use of sunitinib
 - Vaccinations
 - Pregnancy.

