8.1.2 Analysis Of Survival Data

OS, PFS and treatment duration will be analyzed using Kaplan-Meier plots. Median, 25% and 75% survival times with confidence intervals for OS and PFS will be presented. For stratification according to physician's prognosis and for risk groups according to Motzer score/MIPI/Fletcher risk table, log-rank tests will be performed.

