1.3-1.4	Tumor anamnesis - other information	GIST	SAFETY, EAS	.1 Frequency table for size of primary tumor, sample statistics for number of mitoses, frequency table for primary mutation analysis performed?, frequency table for type of KIT-mutation .2 Frequency table for mutation analysis performed in recidive?, frequency table for type of mutation
CCI				
1.3-3	ECG	mRCC, GIST	SAFETY, EAS	Frequency tables for normal/abnormal ECG by time window

Table No.	Title	Treatment/ Indication	Analysis set	Description
CCI				

Table No.	Title	Treatment/ Indication	Analysis set	Description
CCI				
				, number of transplantations, R0 resection reached

Table No.	Title	Treatment/ Indication	Analysis set	Description
CCI				

Table No.	Title	Treatment/ Indication	Analysis set	Description
CCI				
2	Effectiveness			
2.1	Response to therapy			
2.1-1	Course of response to therapy	All	EAS	Frequency table by time window (in total and by patient risk groups)

Table No.	Title	Treatment/ Indication	Analysis set	Description
2.1-2	Best response	All	EAS	Frequency table for best response in total and confirmed / not-confirmed (the latter not for Torisel® MCL); Frequency table for best response excluding patients "not assessable" only for MCL Listing of reasons for not assessable best response; Frequency table for best response by patient risk groups
2.1-3	Used diagnosis technique	All	EAS	CT, Thorax X-ray, MRT, Ultrasonic testing, PET, Bone scan, Clinical (by time window and for best response)
2.2	Overall survival			
2.2-1	Kaplan-Meier estimates for Overall survival	All	EAS Sequence analysis	Time to 25%, median and 75% survival with confidence intervals incl Kaplan-Meier curve on all patients
2.2-2	Kaplan-Meier estimates for Overall survival by patient risk groups	mRCC	EAS	 .1 Physicians prognosis of patients risk .2 Risk groups according to Motzer score .3 Risk groups according to modified Motzer score .4 Risk groups according to Motzer score for pretreated patients .5 by treatment sequence .6 by treatment and treatment line. .7 1st line patients by risk (poor vs. non-poor) .8 by LDH ≤ 300 U/l vs > 300 U/l incl. Log-ranktest and Kaplan-Meier curves

Table No.	Title	Treatment/ Indication	Analysis set	Description

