In case an event (either death or progression) was present and date of event was documented, the following definitions was used:

Overall Survival (OS, months) = $\frac{\text{date of death} - \text{date of baseline visit} +1}{365.25 *12}$

Progression Free Survival (PFS, months) = (minimum of (date of death, date of progression) – date of baseline visit + 1)/365.25 * 12.

In case information on dates were partly or completely missing or contradictory, the following was done:

• PFS:

- o the presence of a progression was confirmed, but no date was documented: if date of last intake of study medication was given, this date was used as date of progression, otherwise the date of the last visit with a documented "non-progression (e.g. SD)" was used as date of progression.
- o the presence of a progression was confirmed, but dates within a visit and on final documentation were contradictory, the prior date was used.
- o in case a death was documented within a survival follow-up/ within sequence 2 for subjects from sequence 1, but no progression was documented within regular study, the date of last visit + 1 day was used as date of progression.
- o in case no progression was documented, subject was censored with the latest available contact date / assessment date within study/within sequence.
- o in case these rules led to a missing duration or a negative duration, duration was set to "1 day".

• OS:

- o in case a death was documented, but date of death was unknown, the date of death was substituted with the latest available date for the patient (last visit, last contact date, date of assessment)
- o in case no death was documented, subject was censored with the latest available contact date / assessment date within study.
- o in case these rules led to a missing duration or a negative duration, duration was set to maximum of (PFS,"1 day").

Response to therapy (Recist criteria/ Cheson criteria)

Response to therapy according to the Recist/ Cheson criteria will be analyzed using the physician's assessment as documented in the CRF. As neither "size of lesion", "new lesions" or "increase in size" are defined as key fields, contradictory answers will not overvote physicians assessment.

"Best response" will be analyzed using the physician's assessment at final visit. If "Best response" is missing it will be determined from the best response documented during previous follow-up visits.

Treatment

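### mRCC overall survival by treatment sequence runs from the baseline visit but is grouped by therapy started later, so first-line patients in the further-therapy groups carry guarantee time

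*SAP*

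**What the plan says.** SAP section 5 lists the mRCC tables to be repeated by treatment sequence, including "overall survival (2.2-1), progression free survival (2.3-1), course of Karnofsky performance scale (2.5". Table 2.2-1 gives the quartiles and median of OS with confidence intervals, and a Kaplan-Meier curve. Two pairs of the listed groups are mutually exclusive and are separated only by what happened after first line:

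- Sunitinib first, followed either by "any further therapy (no axitinib in" second line) or by "no further therapy".
- Temsirolimus first, followed either by any further therapy or by none.

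In SAP Appendix A1.3 the line beginning "Overall Survival (OS, months" counts from the baseline visit to death. No other origin is given for sequence analyses. The flow chart in SAP 2.1 keeps the baseline visit of the first Pfizer sequence apart from the baseline at the start of the second Pfizer therapy.

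SAP section 9, Table 2.2-2 (mRCC), also lists OS "by treatment sequence .6 by treatment and treatment line", on a row that ends "incl. Log-ranktest and Kaplan-Meier curves". It does not say which sequence groups are meant. SAP 8.1.2 is narrower: for the physician's prognosis and for "risk groups according to Motzer score/MIPI/Fletcher risk table, log-rank tests will be performed". The OS strata in SAP 8.2.3 do not include sequence. Neither document names a landmark, a second-line clock or a time-dependent method.

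**The concern.** Whether a first-line patient belongs to a further-therapy group is not known at baseline. It is settled only when second line starts, and the patient must be alive then. The wait for second line is guaranteed survival, and the plan counts it as OS for the further-therapy groups. Deaths during that wait are assigned to the no-further-therapy groups by construction.

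Survival time and therapy sequence are both listed as of particular interest (SAP 2.2), and publication is planned (Protocol 12.1). A reader who sets the two curves side by side would see a survival advantage for further therapy that the grouping alone can produce. The protocol's discussion of bias sources covers selection bias and confounders, but not this.

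There is also a second clock. Protocol 7.2, criterion c, enrols patients "after failure of prior therapy with sunitinib or a cytokine for whom a decision was already made to treat with axitinib". Their baseline is the axitinib start, so they carry no first-line guarantee time. The group with any therapy followed by second-line axitinib can therefore mix two time origins, and so can the sunitinib-then-axitinib group if it includes such patients.

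**Working it through.** The plan gives no figure for OS by sequence, so there is nothing to reproduce. The bias follows from the definitions above. Its size is illustrated under no effect of later therapy.

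**Inputs**

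- Five-year stage IV survival of 10% (Protocol 5.2), assumed to apply from baseline with a constant hazard: λ = −ln(0.10)/60 = 0.0384 per month, so median OS = ln 2/λ = 18.1 months.
- Average observation period of 12 months for sunitinib and 6 for temsirolimus (Protocol 6), assumed to be the mean time to death or switch: r = 1/12 or 1/6. The switch hazard is s = r − λ = 0.0450 or 0.1283.
- Recruitment over 156 months (SAP 2.1) and 14 years of data collection (Protocol 6): entry assumed uniform over months 0–156, data cut at month 168.
- Share p of survivors who go on to second line: not given; 1.0, 0.7 and 0.5 assumed.

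**Closed form, p = 1, no censoring**

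- No further therapy: these patients die before switching, so the median is ln 2/r = 8.3 months (sunitinib) or 4.2 (temsirolimus).
- Further therapy: the survival function is [e^(−λt) − (λ/r)e^(−rt)]/(s/r). For sunitinib at t = 31.0 it is (0.304 − 0.035)/0.539 = 0.50. For temsirolimus it reaches 0.50 at t = 24.6.

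The true median in every group is 18.1 months.

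**Kaplan-Meier medians with the assumed entry and data cut (months)**

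| Share switching | Sunitinib: further / none | Temsirolimus: further / none |
|---|---|---|
| 1.0 | 30.5 / 8.7 | 24.6 / 4.3 |
| 0.7 | 30.4 / 12.2 | 24.6 / 10.5 |
| 0.5 | 30.5 / 14.1 | 24.6 / 13.7 |

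Timed from second-line start, the median returns to 18.0–18.1 months.

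**Sensitivity (uncensored)**

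- Assumed overall median OS of 12–36 months: the gap is 14–41 months if all survivors switch, 10–29 if 50–70% do.
- First-line temsirolimus patients need at least 3 of 6 risk factors (Protocol 7.2), so 18.1 months may be generous. At an assumed 8 months the medians are 14.4 and 4.2 (gap 10.2), with gaps of 8–9 months at 50–70% switching.
- If 12 and 6 months are read as mean time to switch alone, a 20-month overall median splits into 29.3 and 5.9 (sunitinib) or 25.4 and 3.4 (temsirolimus).

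**Mixed clocks.** At the same hazard, median OS is 31.0 months for patients followed from sunitinib start, 18.1 for those enrolled at axitinib start, and 24.6 for an assumed half-and-half mix.

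**If a log-rank test is run.** At a nominal 5% (the documents set no alpha), it favours further therapy in 100% of null runs when all survivors switch, and in 46–100% at 50–70% switching (n = 100–200). With a shared log-normal frailty on death and switching (assumed SD 0.5–1.0, n = 200) it still does so in 36–100%.

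**MCL.** Table 2.3-2 compares PFS of responders with that of patients with minor response or stable disease, using a log-rank test. The same mechanism applies only so far as responses are first recorded after the first visits, and the documents give no response timing. With n = 100, median PFS of 3–12 months and a 15–30% response chance per 10-weekly visit (all assumed), null rejection is 5–8% if responses appear only at the first visit and 71–100% if they can appear at any visit. No single figure is claimed.

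**The case against.** The evaluation is purely descriptive (Protocol 11, Biometric evaluation), and SAP 4.1 and 4.2 set no hypotheses or decision rules. A Kaplan-Meier median for patients who received a given sequence does describe that group; the harm lies in comparing groups. It is unclear whether sequence is tested at all, because item .5 of Table 2.2-2 names no groups and SAP 8.1.2 and 8.2.3 point the other way. This stands. The rejection rates above matter only if the test is run, but the medians and curves are distorted either way.

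The size rests on assumptions. The observation period is a planning figure, not a switch time, and one stage IV survival figure is applied to both drugs. This also stands; the direction does not depend on it.

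The baseline visit might be read as that of the second sequence. The OS definition does not say so, and a non-Pfizer second line has no baseline visit, so the any-further-therapy groups would still be affected.

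Second-line start dates may be missing. Start dates are used in the therapy-line rules (SAP A1.3), but those appear to count earlier lines. Interim non-Pfizer data are analysed only under Amendment VI (SAP 7), with 17 patients in interim documentation by September 2020 (Protocol 11). The survival sheets record tumour therapy, but no start-date field is shown. This limits the second-line analysis. It does not rescue the baseline-timed contrast.

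**Conclusion.** The concern holds. Following the plan as written builds guarantee time into baseline-timed OS for first-line patients grouped by later therapy, and makes further therapy look better. That direction is certain from the definitions. The size is illustrative: about 20–22 months between medians in the main illustration if every survivor switches, 11–18 at 50–70% switching, and still 8–10 months for temsirolimus if overall median OS is only 8 months. These figures rest on constant hazards, the stated proxies and no therapy effect.

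No decision rule depends on the result, so this should be fixed but does not threaten the registry. The Amendment VI sequences are only listed (SAP 5) and are not affected. The MCL point is conditional on response timing.

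**What to change.** - Define mutually exclusive groups for item .5 of Table 2.2-2, say whether a sequence ending in any further therapy can include none, and say whether sequence is tested.
- Drop baseline-timed comparisons, curves or tests, of further-therapy with no-further-therapy groups.
- Report OS from baseline by first documented therapy, without splitting on later therapy.
- Report OS from second-line start among patients who start it. Patients enrolled at axitinib start in second line then share the same clock. Count and report those without a dated start.
- If switchers and non-switchers are still contrasted, use a landmark or a time-dependent switching term.
- State that this removes guarantee time only. Documentation of a therapy ends with change or discontinuation for progression or intolerance (Protocol 11), so confounding remains and the results are not causal.
- For MCL response, use a week-15 landmark (end of Treatment Phase 1, SAP A1.1) or time-dependent response, with the same caveat.

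The core change costs SAP wording and the reprogramming of a few tables. The second-line analysis also depends on dates that may be incomplete. In the illustration it keeps 26–52% of first-line sunitinib and 38–77% of first-line temsirolimus patients, and it does not show whether further therapy prolongs life.

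A 6-month landmark keeps about 79% of patients. It rejects in 5–7% of null runs if switching is independent of prognosis, but in about 15–37% with frailty SD 0.5 and 45–93% with SD 1.0, almost always against further therapy. It is not a clean test. The MCL landmark keeps about 45–82% of patients under its assumptions.
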